5.2.2 Blueberry anthocyanins (VitaBlue): Similarly, there is no established Dietary Reference Intake of the constituents of anthocyanins. The average daily consumption of anthocyanins in a western diet is estimated to be 100 mg/day.¹²⁰ Anthocyanins are rapidly absorbed and metabolized extensively following a moderate-to-high oral dose in humans. Studies have indicated anywhere from 4-6 hours half-life with complete excretion of parent compound as well as metabolites within 24 hours both in urine and plasma, indicating the need for a dose every 6- 8 hours to have consistent exposure¹²¹. Similarly administration of anthocyanins at doses ranging from 0.5-2.0 grams daily for 7 days in colorectal cancer patients with dose dependant concentrations detected in plasma and urine with no toxicities.¹²⁰ Studies utilizing anthocyanins at doses of 1.4 grams/day (Mitroslect, Indena S.p.A.) administered as 0.47 grams/capsule TID are currently in progress to provide active cellular antioxidant protection, inhibit inflammatory gene expression and consequently protect against oxidant-induced and inflammatory cell damage and cytotoxicity in obesity-induced inflammation and insulin resistance (NCT01180712) in 40-60 year old males for 21 days. In summary, repeated administration of anthocyanins exerts pharmacodynamic effects and generates concentrations of anthocyanins in human plasma as well as urine with no toxicity. We will thus use a dose of 0.47 grams/capsule dose of anthocyanins TID to total 1.4 grams per day, similar to the dose used in these chemoprevention trials.

5.3 Availability: VitaBlue will be obtained from VDF FutureCeuticals'. The product has earned self-affirmed GRAS (generally recognized as safe) status for use in food and beverages after a comprehensive review by an independent panel of experts. Lovaza® is manufactured and distributed by Glaxo Smith-Kline laboratories and will be obtained from them for use in this study. The capsules have been manufactured by our team utilizing standards established by the FDA in a certified Compounding Center (Carrollwood Compounding Center and Pharmacy) and verified by the Center and by an independent testing group to assure consistent quality of the active agent contained in each capsule. The FDA has verified all these aspects of the agent as well as the placebo manufactured for this study and has provided us an IND approval of

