6.1 Dose Regimen and Dose Groups: Intervention groups

6.1.1 Placebo Group: All participants in the placebo arm will receive the multivitamin supplement and the cognitive battery tests and structural and resting-state functional imaging at baseline and 3 months. The placebo group used herein will allow us to generate information regarding the reliable change index, so information regarding the naturalistic change in cognitive performance, as well as the potential for practice effects to influence mean-level change data, across the follow-up period is important.

6.1.2 Nutritional Supplement Group (NS): The choice of the supplement to use in this trial is based on relevant research supporting the various components as well as the use of a commercially available standardized dietary supplement of anthocyanins and n-3 fatty acids. The supplement to be used is a standardized formulation of blueberry extract VitaBlue® (40% polyphenolics, 12.5% anthocyanins from blueberries. The supplement will in addition include Lovaza® (omega-3-acid ethyl esters), an FDA-approved prescription omega-3 provides prescription-only potency and purity with each 1-gram Lovaza® (omega-3-acid ethyl esters) gel capsule contains 90% omega-3-acid ethyl esters; 84% eicosapentaenoic acid (EPA) and docosahexaenoic acid (DHA) ethyl esters. Lovaza® is provided by GlaxoSmithKline, who has authorized the FDA center for Drug Evaluation and Research, Division of Metabolic and Endocrine Drug Products to reference Lovaza® Capsules IND # 45,998. An investigator-initiated IND has been obtained by PI for use of these agents in this clinical trial (IND # 116424). Subjects in the supplements treatment arm of the study will be given in the same fashion and time table to the "placebo" patients as the active treatment patients.

6.2 Agent Administration: Intervention will be administered to the patient on an outpatient basis and self-administered by the participants. The daily dose of will be taken in divided doses (Lovaza® 2 tablet BID and Vitablue™ 2 tablet TID). On the day of monthly follow-up visit, capsules should be taken within 4 hours of visit and blood draw for required lab work.

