Two bottles containing Lovaza and 1 bottle of anthocyanins capsules will be dispensed to all participants upon randomization with adequate number of capsules, to ensure that the subject has sufficient study drug to last until the next planned clinic visit. At baseline and at each monthly visit up to the 3-month final visit, participants will receive these supplements in person to take home with them. At that point, participants will receive instructions regarding how many supplement pills they are to take a day.

Schedule of dose administration of study agents

Arm of Study	Breakfast	Lunch	Dinner
Treatment arm	2 tablets Lovaza 2 tablets Vitablue	2 tablets Vitablue	2 tablets Lovaza 2 tablets Vitablue 1 tablet multivitamin/mineral
Placebo arm	4 tablets matching placebo tablets	2 tablets matching placebo	4 tablets matching placebo tablets 1 tablet multivitamin/mineral

6.3 Contraindications: COGNUTRIN ingredients - n-3 fatty acids may be contraindicated in subjects with bleeding disorders and anthocyanins may be contraindicated in people who are sensitive or allergic to berries.

During study participation, subjects will be instructed to limit their consumption of the following berries to 1 cup per day: blackberry, blueberry, chokeberry, black currant, elderberry, and black raspberry. They will be asked to limit their consumption of the following omega 3's to 2-3 servings (4 oz per serving) a week: walnuts, flaxseed oil, canola oil, fish oils, and fatty fish such as salmon, trout, mackerel, herring, sardines, pilchards, kipper, eel, whitebait, fresh tuna, anchovies, swordfish, bloater, cacha, carp, hilsa, jack fish, katla, orange roughy, and pangas.

6.4 Concomitant Medications: During study participation, subjects will be instructed to suspend consumption of additional supplements containing anthocyanins or omega 3's. Subjects are considered enrolled in the trial from the time that the informed consent document is signed until the time that the subject is off study. All medications (prescription and over-the-counter), taken by the participant while on study will be documented on the concomitant medication CRF and will include: start and stop date, dose and route of administration, and indication.

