7.7.13 Inflammatory markers-Cytokines will be measured with a panel including IL-1, IL-4, IL-6, IL-8, IL-10, IL-12, GM-CSF, IFN-gamma, TNF α , and CRP (BioRad-Bioplex). All of these biomarkers have been shown to increase with disease, aging and cytotoxic agents and will be used to monitor compliance with the dietary supplementation group and as a covariate in the analysis of cognitive function. The cytokine panel will be completed by [name] in her research laboratories.

One 10 ml of blood will be collected in a purple top (EDTA) vacutainer and centrifuged at 3000 RPM /10 minutes/ RT for isolation of PBMC, plasma and RBC. Approximately 5 ml of plasma will be collected and placed into one labeled screw cap tube and frozen at -80C. The Buffy Coat with adjacent layer of plasma & RBC will be harvested and transferred to 50 cc conical tube with 10ml of PBS. The remaining RBC will be harvested and washed 3 times with PBS and then re-suspended in equal volume of distilled water. Two, 1 ml RBC aliquots will be placed in labeled screw cap tubes and frozen in at -80C. Harvested BC will be harvested on Ficoll for PBMC (no cell count required). PBMC will be washed once in PBS and the cells will then be re-suspend in 2ml of Freezing Media (40 ml FBS + 7 ml DMSO + 3 ml RPMI). Two, 1ml aliquots of PBMC will be placed in labeled cryovials, and frozen MR. Once frosty, they will be placed in storage. All samples will be stored in the Tissue Core at Moffitt Cancer center until analysis.

2 - 10 ml tube will be forwarded to Tissue Core labs at the Moffitt Cancer Center for processing and storage. Once labs specimens for 40 subjects (pre and post intervention) have been collected, they will be transported from Tissue to [name] lab at USF and [name] lab at MCC by the clinical research coordinators, using appropriate containers to preserve the temperature and thus integrity of the specimens for assay of oxidative stress markers.

The plasma collected for assay of oxidative test markers and cytokines will be stored for a maximum of 12 months at -80°C. All specimens collected for assay of safety markers (CBC, CMP, PT, PTT, and LDL) will not be stored as they will be completed in real time.

7.7.14 Magnetic Resonance Imaging: Structural and Resting-state functional MRI (fMRI):

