12.6 Evaluation of Toxicity

The primary safety endpoint is incidence and severity of AEs occurring during intervention with either COGNUTRIN or placebo. All participants will be evaluated for toxicity from the time that the informed consent is signed up to the end of the intervention according to the NCI CTCAE version 4.0. Standard assessment of toxicity will also include interviews, clinical evaluation, and monitoring of laboratory values. All toxicity data will be summarized by category and grade in a standard fashion. Proportions experiencing most common types of toxicity in this trial will be estimated and exact 95% CIs calculated based on the exact binomial distribution for these proportions will be reported. Compliance will be evaluated by standard pill counts, diet records and plasma levels of anthocyanins and erythrocyte n-3 index. Any unusual patterns in compliance will be noted and apparent discrepancies between pill counts or diet records and plasma levels by will be summarized as well.

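### Plasma anthocyanin shows roughly the last day's intake and cannot check three months of adherence; cytokines are not an exposure measure; neither blood marker named for compliance has an assay or sample

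*Combined protocol and SAP*

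**What the plan says.** Sections 12.5.3 and 12.6 carry the same sentence: "Compliance will be evaluated by standard pill counts, diet records and plasma levels of anthocyanins and erythrocyte n-3 index". Both add that mismatches between plasma levels and the pill counts or diet records will be summarised.

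Other sections bear on what those levels can show:

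- Section 5.2.2 describes anthocyanins as having "anywhere from 4-6 hours half-life with complete excretion of parent compound as well as metabolites within 24 hours both in urine and plasma". Section 6.5 repeats this.
- Section 6.2: "On the day of monthly follow-up visit, capsules should be taken within 4 hours of visit and blood draw for required lab work". VitaBlue is taken three times a day.
- Table 1 schedules research blood at screening and week 12 only, and labels it for oxidative stress and cytokines. Sections 7.7.12 and 7.7.13 describe those assays and no others.
- Section 6.3 tells women to "limit their consumption of the following berries to 1 cup per day", a list that includes blueberries.
- Section 7.7.13 says of the cytokine panel that it "will be used to monitor compliance with the dietary supplementation group". Sections 8.2 and 12.5.1 make the cytokines candidate mediators of the cognitive effect.
- Section 7.7.13 also banks red cells: "Two, 1 ml RBC aliquots will be placed in labeled screw cap tubes and frozen in at -80C". No purpose is given for them.
- Section 6.6 expects at least 85% of study agent to be taken and verifies this by monthly pill counts. Section 7.7.6 adds a daily intake log.

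**The concern.** A biochemical marker is useful beside pill counts because it does not depend on what a woman returns or writes down. For that it must reflect intake over a period like the one the pill count covers. A marker cleared within a day, sampled soon after an instructed dose, does not. A woman who missed most doses but took the visit-day one would look much like a full adherer. A woman who took everything until two days before the draw would look like a non-taker. The planned list of mismatches would then largely record when the last capsule, or the last cup of berries, was taken.

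Cytokines have a different problem. They are a hypothesised response to the supplement, so a woman who took every capsule but did not respond would appear non-compliant.

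This matters because section 3.0 presents the trial as a feasibility pilot for a larger study and lists biomarker methods and effect sizes among what it should deliver. A misleading adherence check would be carried into the next design.

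**Working it through.** The plan gives no figure for this marker, so there is none to reproduce. The check uses the plan's own half-life.

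**Inputs from the documents.** Half-life h of 4 to 6 hours (5.2.2); three VitaBlue doses a day (6.2); a dose within 4 hours before the draw (6.2); one on-treatment research sample, at week 12, since screening precedes dosing (Table 1).

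**Assumptions, not in the documents.** First-order elimination, equal doses, immediate absorption, a morning visit with the breakfast dose as the last dose before the draw, and the meal times tabulated below. Dose size cancels.

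**Step 1: consistency with the stated clearance.** The fraction of a dose left after t hours is 2^(-t/h).

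- 24 h: 2^(-24/4) = 1.6%; 2^(-24/6) = 6.3%. This fits the plan's statement of clearance within a day.
- 48 h: 2^(-48/4) = 0.02%; 2^(-48/6) = 0.4%. A woman who stops two days before the draw has almost nothing left from earlier doses.

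**Step 2: visit-day dose only against full adherence.** Let c be the carry-over from all earlier doses at breakfast on the visit day, in units of one dose:

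c = sum over earlier days d = 1, 2, … and dose times s of 2^(-(24d - s)/h)

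The visit-day-only level divided by the full adherer's level is 1/(1 + c). Time from breakfast dose to draw cancels, because both levels decay by the same factor.

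Example with doses 0, 5 and 11 hours after breakfast and h = 4: the previous day contributes 2^(-24/4) + 2^(-19/4) + 2^(-13/4) = 0.0156 + 0.0372 + 0.1051 = 0.158. Dividing by (1 - 2^(-24/4)) to include all earlier days gives c = 0.160, and 1/1.160 = 86%.

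| Dose times, hours after breakfast | h = 4 | h = 5 | h = 6 |
|---|---|---|---|
| 0, 5, 11 | 86% | 78% | 70% |
| 0, 4, 10 | 88% | 80% | 72% |
| 0, 6, 12 | 84% | 76% | 68% |
| 0, 8, 16 | 75% | 67% | 60% |

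The range is 60 to 88%. Equivalently, a full adherer's level is only 1.14 to 1.66 times that of the visit-day-only taker. Over 12 weeks that taker has swallowed 1 of 84 × 3 = 252 scheduled VitaBlue doses.

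**Step 3: how well a threshold could separate them.** The plan sets no threshold, so this is illustration only. Assume log-normal between-subject variation with CV 30 to 80%, s = sqrt(ln(1 + CV²)), and a cut-off that 95% of full adherers pass. The share of visit-day-only takers who also pass is 1 - Φ((ln(1 + c) - 1.645 s)/s). With doses at 0, 5 and 11 hours this runs from 67% (h = 6, CV 30%) to 92% (h = 4, CV 80%). Over all four schedules it runs from 47 to 93%.

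**Step 4: promise against provision.** Sections 12.5.3 and 12.6 promise two blood markers. Neither plasma anthocyanin nor the erythrocyte n-3 index has a row in Table 1, an assay in sections 7.7.11 to 7.7.13, or a named sample. Nothing in those sections has time since last dose recorded at the draw.

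**The case against.** The strongest reply is that the plan asks little of this marker. There is no plasma cut-off, nobody is labelled compliant or non-compliant by it, and the 85% expectation is checked by pill counts with a daily log alongside. No endpoint or analysis population depends on it: section 12.7 assesses every participant for response, even after major deviations. All of that stands, and it bounds the point.

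A reader might infer that non-takers will be called compliant. The documents do not support that. A woman who also skips the visit-day dose has no supplement-derived level, and no rule turns a level into a label. Nor does the level show the visit-day dose alone: in the schedules above, 12 to 40% comes from earlier doses. It is also too strong to say that a null cognitive result could not be told apart from non-intake, because pill counts and logs would still bear on that.

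The instruction in section 6.2 refers to monthly visits and required lab work and does not mention an anthocyanin assay. The calculation therefore describes what would happen if anthocyanin were measured on the scheduled week-12 sample, which the plan does not actually say.

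Berry intake is partly covered. Section 7.7.4 gives the diet record the purpose of detecting over-consumption of similar products, and section 12.6 brings diet records into the comparison. A two-day record once a month may still miss berries eaten just before the draw.

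Finally, a near-zero level in a treated woman with a perfect pill count, at a visit where she was told to dose, is informative about recent intake. That argues for reporting the marker under the right label, not for discarding it.

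**Conclusion.** The point holds as a limit on what the planned check can show. On the protocol's own half-life and dosing instruction, plasma anthocyanin is a marker of recent intake: mostly the visit-day dose, and at most about the last day. A visit-day-only taker would show about 60 to 88% of a full adherer's level, so reading it against cumulative pill counts says little about three-month adherence. In the placebo arm it says nothing about capsule-taking. The percentages rest on the assumed meal times, a morning visit and simple elimination; the qualitative conclusion needs only the stated half-life and 24-hour clearance.

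Two conclusions need no calculation. Cytokines cannot serve both as a compliance monitor (7.7.13) and as the hypothesised mediator (8.2, 12.5.1) without treating non-response as non-compliance. And both blood markers promised in 12.5.3 and 12.6 lack an assigned assay and sample.

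The documents give no red-cell n-3 turnover and do not say that the banked aliquots suit that assay, so any advantage of the n-3 index is an assumption.

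**What to change.** 1. In 6.6, 12.5.3 and 12.6, state that pill counts define the 85% expectation.
2. Report plasma anthocyanin, if assayed, only as a marker of recent intake. Name the assay and sample, and record time since last dose and recent berry intake at the draw. Do not read it against cumulative pill counts as a check on three-month adherence.
3. In 7.7.13, delete cytokines as a compliance measure and keep them as outcome and candidate mediator.
4. Assign the erythrocyte n-3 index to the banked screening and week-12 red-cell aliquots, compared by arm, as the biochemical check for the Lovaza component. First confirm that aliquots washed and re-suspended as 7.7.13 describes suit the assay, and state as an assumption that the index reflects longer-term intake.

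The cost is protocol and analysis wording, two items on the visit form, and some work to specify the assays and laboratory. The red cells are already planned for banking, so the n-3 index needs no extra blood draw, and no dosing instruction changes. What remains unsolved is a long-term biochemical check on VitaBlue intake, which the current plan does not provide either.

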12.7 Evaluation of Response

All participants included in the study will be assessed for response to intervention, even if there are major protocol deviations. We estimate that a minimum evidence of improvement in cognitive function with the 3 month intervention as indicated by a score of 1 standard deviation or more above population norms on the Hopkins Verbal Learning Test – Revised, Controlled Oral Word Association Test, or Color Trails Test Part 1 or 2 will be considered adequate to justify progression to a larger study.

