8.1 Primary Endpoint

The primary efficacy endpoint is to generate effect sizes for changes in the number of impaired neuropsychological tests. The planned intervention period is three months. Neuropsychological outcomes will be examined using a 2 (group; COGNUTRIN, placebo) X 2 (time; baseline, three-months) repeated measures ANOVA to examine differences in the number of impaired neuropsychological tests. Age, premorbid cognitive functioning, depression and fatigue will be evaluated for association with neurocognitive performance and entered as covariates in statistical analyses if a marginally significant association ($p < .10$) is observed.

The primary safety endpoint is incidence and severity of AEs occurring during intervention with either COGNUTRIN or placebo. All AEs that are reported by the subject, detected during a visit, physical examination, or laboratory work-up will be recorded in the participant's medical record and recorded on the CRF. All AEs that occur after the informed consent is signed will be recorded on the AE CRF whether or not related to study agent.

The sample size proposed in the current protocol will not provide sufficient statistical power, but information regarding effect sizes will be gathered and used as motivation for future clinical trials. We estimate that a minimum evidence of improvement in cognitive function with the 3 month intervention as indicated by a score of 1 standard deviation or more above population norms on the Hopkins Verbal Learning Test – Revised, Controlled Oral Word Association Test, or Color Trails Test Part 1 or 2 will be considered adequate to justify progression to a larger study.

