12 STATISTICAL CONSIDERATIONS

12.1 Study Design/Endpoints

The central hypothesis for this Pilot clinical trial is that adults who receive COGNUTRIN will exhibit reduction in the number of impaired cognitive tests, as compared to adults on the placebo.

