12.2 Sample Size/Accrual Rate

In this pilot trial, we plan to accrue 40 evaluable subjects. This is a feasibility clinical trial in preparation to inform the design of a well-powered randomized clinical trial.

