12.4 Primary Endpoint

The primary efficacy endpoint is to generate effect sizes for changes in the number of impaired neuropsychological tests. The planned intervention period is three months. Neuropsychological outcomes will be examined using a 2 (group; COGNUTRIN, placebo) X 2 (time; baseline, three-months) repeated measures ANOVA to examine differences in the number of impaired neuropsychological tests. Age, premorbid cognitive functioning, depression and fatigue will be evaluated for association with neurocognitive performance and entered as covariates in statistical analyses if a marginally significant association ($p < .10$) is observed.

The primary efficacy endpoint is to generate effect sizes for changes in the number of impaired neuropsychological tests. The planned intervention period is three months. Neuropsychological outcomes will be examined using a 2 (group; COGNUTRIN, placebo) X 2 (time; baseline, three-months) repeated measures ANOVA to examine differences in the number of impaired neuropsychological tests. Age, premorbid cognitive functioning, depression and fatigue will be evaluated for association with neurocognitive performance and entered as covariates in statistical analyses if a marginally significant association ($p < .10$) is observed. The sample size of 20 patients per arm will allow us to generate useful information for future studies, in terms of anticipated effect size. Although this pilot study is not designed to be fully powered, the current sample size will allow us to detect an effect size difference of .40 for a one-tailed paired sample t-test, on account of the matched groups, at power of .80 and an alpha of .05. Moreover, the sample sizes will enable us to detect a group X time interaction of .23, with an alpha of .05, power of .80, and a stability coefficient of .5.

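### The numeric progression threshold is an absolute score level with no baseline, placebo comparison, unit or number of patients, and it is not tied to the group-by-time effect size that the plan already estimates

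*Combined protocol and SAP*

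**What the plan says.** Sections 8.1 and 12.7 carry the same sentence. Its threshold is performance "indicated by a score of 1 standard deviation or more above population norms on the Hopkins Verbal Learning Test"; the other qualifying tests are the COWA (the oral word association test) and the two parts of Color Trails. Reaching that level on one of the four counts as "a minimum evidence of improvement in cognitive function with the 3 month intervention", and the plan adds that this "will be considered adequate to justify progression to a larger study". The sentence gives no baseline value, change score or arm. It does not say whether the unit is a woman or an arm mean, or how many women are needed. Section 12.7 says that every participant will be assessed for response, but not how the two arms' results are then used.

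The rest of the plan is comparative:
- Section 12.1 states the hypothesis that "adults who receive COGNUTRIN will exhibit reduction in the number of impaired cognitive tests, as compared to adults on the placebo".
- Section 6.1.1 gives natural change and "the potential for practice effects to influence mean-level change data" as reasons why the placebo group matters.
- Sections 8.1 and 12.4 analyse the count of impaired tests with a "2 (group; COGNUTRIN, placebo) X 2 (time; baseline, three-months) repeated measures ANOVA". Just before the threshold, 8.1 says that effect sizes will be used to motivate later trials.
- Section 7.7.9 defines impairment in the opposite tail, at least 1 SD below norms.
- Section 4.0 bases entry on subjective complaints and notes that their link to test performance is not well established.

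**The concern.** This is the one place where the pilot attaches a number to the decision it exists to inform. A post-treatment level cannot separate a product effect from where the women started, retest noise or practice. No entry criterion stops a woman from scoring 1 SD above norms on one of the four tests at baseline and later being counted as improved. The threshold also looks at a different part of the scale from the primary endpoint: a woman can move from impaired to unimpaired without coming near it.

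At stake is a decision to run a larger trial on evidence that an inert product could produce, while the placebo contrast that the trial already pays for has no stated role in the threshold.

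**Working it through.** The plan states no false-go rate or power for this threshold, so there is no figure of its own to reproduce. Its behaviour can be calculated under stated assumptions.

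**Inputs from the documents.** Threshold +1 SD; any of four tests (8.1, 12.7); 20 per arm (12.4); "power of .80, and a stability coefficient of .5" (12.4); "we plan to accrue 40 evaluable subjects" (12.2).

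**Assumptions.** Normal scores in SD units from norms; one score per test; group mean 0, -0.5 or -1; inter-test correlation 0, 0.3 or 0.5. Retest correlation .5 is borrowed from the stability coefficient in 12.4, which is not a single-test retest value. There is no treatment effect in steps 1 to 3.

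**1. Share of women at or above the threshold (level reading).** With independent tests, P = 1 - (1 - Φ(mean - 1))^4.
- Mean 0: 1 - (1 - 0.1587)^4 = 0.499
- Mean -0.5: 1 - (1 - 0.0668)^4 = 0.242
- Mean -1: 1 - (1 - 0.0228)^4 = 0.088

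Positive correlation lowers these values (numerical integration).

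**2. Share newly crossing** (at or above +1 SD at month 3 and below it at baseline on the same test; simulation).

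| Mean | Level, correlation 0 / 0.3 / 0.5 | Newly crossing, correlation 0 / 0.3 / 0.5 |
|---|---|---|
| 0 | 0.499 / 0.425 / 0.373 | 0.332 / 0.295 / 0.265 |
| -0.5 | 0.242 / 0.211 / 0.185 | 0.180 / 0.162 / 0.145 |
| -1 | 0.088 / 0.080 / 0.072 | 0.073 / 0.067 / 0.061 |

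At mean 0, a retest correlation of .7 to .8 still gives 0.19 to 0.27 newly crossing.

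**3. If one treated woman of 20 were enough** (the text gives no number), P = 1 - (1 - p)^20.
- Level: over .999 at mean 0, .98 to .996 at -0.5, .77 to .84 at -1.
- Newly crossing: over .99, .96 to .98, .71 to .78.

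**4. Arm-mean reading, with a real effect.** The SE of a mean of 20 is 1/√20 = 0.224. If the true mean rises from norms to +0.5 SD on all four tests, each test passes with probability P(Z ≥ 0.5/0.224 = 2.24) = 0.0127. Any of four independent tests gives 1 - (1 - 0.0127)^4 = 0.050; correlation 0.3 and 0.5 give 0.046 and 0.042.

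**5. What the existing contrast offers.** Take the between-arm difference in change, in baseline SDs of the impaired-test count, unadjusted, with correlation .5. SE = √[(2/20) × 2 × (1 - .5)] = 0.316. The 95% half-width is 2.024 × 0.316 = 0.64. At 18 per arm (40 randomised, 10% lost as section 4.3 expects) it is 0.68. Pass rates for an estimate of at least X (normal approximation):

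| X | No effect | True benefit 0.5 SD of the count |
|---|---|---|
| 0.2 | 26% | 83% |
| 0.3 | 17% | 74% |
| 0.5 | 6% | 50% |

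These are SDs of the count. The 0.5 SD in step 4 is per test, so the two sets of pass rates must not be compared.

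**The case against.** The best defence is that the sentence does not stand alone. In 8.1 it follows a statement that effect sizes will motivate future trials, and those come from a placebo-controlled ANOVA. Section 3.0 adds feasibility inputs. It would therefore be wrong to call the threshold the only basis for progression. What stands is that it is the only one with a number, and that it is not connected to the contrast beside it.

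A reader might infer that no reading of the rule can isolate a product effect. The text does not support that. Section 12.7 assesses all participants, and the hypothesis is comparative, so responders could be tabulated by arm. That reading is open, but it is not stated.

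A reader might also infer from step 4 that the rule would stop a useful product. The wording makes the threshold sufficient, not necessary, and nothing says that missing it blocks a larger trial. The arm-mean figure shows only that this reading is uninformative.

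The near-certain pass rates in step 3 need a one-woman trigger that the documents never state. The per-woman shares do not need it, but they depend on the assumed mean and correlations. They also assume one score per test, whereas 7.7.9 derives four HVLT-R measures and the threshold does not say which counts.

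Finally, this is an openly underpowered pilot. That excuses imprecision, but not a progression threshold without a stated comparator.

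**Conclusion.** The concern holds in a limited form. The threshold is an absolute level that women can meet without any product effect: 37 to 50% at norms, 18 to 24% at -0.5 SD and 7 to 9% at -1 SD. Requiring a new crossing lowers this only to 27 to 33%, 14.5 to 18% and 6 to 7%. If one treated woman of 20 sufficed, an inert product would pass with probability from about .71 to over .99. As an arm mean, the threshold is rarely met even with a moderate real gain. These figures rest on normal scores, inter-test correlation 0 to 0.5 and, for new crossings, an assumed retest correlation of .5.

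The documents do not support going further. They do not make the threshold a condition for progression, do not rule out a by-arm responder comparison, and do not let it affect the primary ANOVA. It should be fixed because it bears on what the pilot is for and the repair is small.

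**What to change.** In 8.1 and 12.7, replace the threshold with:

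> Progression will be judged on the placebo-minus-COGNUTRIN difference in baseline-to-month-3 change in the number of impaired tests, estimated from the section 12.4 model with the same covariates as the primary analysis, signed so that positive means benefit, divided by the pooled baseline SD of the count, with its 95% CI, against a minimum value X that the sponsor fixes before unblinding. This is an estimate, not a significance test.

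The covariate clause is needed because 12.4 admits covariates at p < .10 and 7.7.9 makes the adult reading test a covariate in all cognitive comparisons. An unadjusted difference might therefore not match the primary result. The table in step 5 of the working can guide the choice of X; it is unadjusted and for orientation only.

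The cost is wording in two sections, with no new data or visits. The downsides are that X must be fixed in advance, progression may be harder to claim, and the estimate stays imprecise at this sample size.

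Two separate minor points could be settled in the same amendment. Section 7.7.9 uses both a CA- sample, which this trial does not enrol, and population norms to classify impairment. Also, the Color Trails text in 7.7.9 promises alternate forms at follow-up, while Table 1 in 7.1 lists Form A at both visits; the two must be reconciled.
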